1.0 Introduction and Background

Breast reconstruction defines the final step for many women on a long road to recovery from breast cancer. Reconstruction of the breast mound following mastectomy has several benefits in psychosocial functioning, body image and satisfaction with breast appearance, and sexual well-being¹⁻⁴. However, reconstruction at the same time as mastectomy has been linked to higher post-operative pain⁵. As in any surgical procedure, post-operative pain control has a major impact on patient satisfaction and important outcome measures such as length of stay, readmission rates, and overall hospital costs⁶⁻⁸. In particular, poor post-operative pain control in the cancer population has a negative impact on physical functioning, with decreased ability to perform activities of daily living, social functioning, with decreased interest in hobbies and contact with friends, and can increase feelings of anxiety and depression⁹. In fact, fear of post-surgical pain has been shown to be a major reason that women refuse breast reconstruction surgery¹⁰.

Implant based breast reconstruction is a widely used and well accepted technique with 86,013 procedures performed in the United States in 2015 vs 20,325 flap based breast reconstruction procedures¹¹. However, this technique has disadvantages in relation to post-operative pain. Compared to autologous breast reconstruction, implant based techniques have been linked to higher requirements of post-operative benzodiazepines, nonsteroidal anti-inflammatory drugs, and narcotics as well as higher pain scores in the immediate post-operative period and one year after surgery^{5,12}. Tissue expander based techniques in particular lead to even higher narcotic use and morphine equivalents than single staged implant reconstruction⁵.

In an effort to decrease pain control, it is common practice for local anesthetics to be infiltrated into the surgical wound. Individual studies have shown that infiltrations with bupivacaine specifically have decreased intraoperative and postoperative narcotic use, decreased pain scores in the immediate postoperative period²⁴⁻²⁶. However, upon meta-analysis of randomized clinical trials studying the effect of wound infiltration with bupivacaine or ropivacaine it was found that postoperative pain severity was only decreased at 2 hours postoperatively and postoperative analgesic consumption did not change²⁷. In light of this, there continues to be a need for improvement in postoperative pain management for mastectomy and subsequent breast reconstruction.

One such medication which has been suggested for improvement in pain control after mastectomy and breast reconstruction is Exparel (Pacira Pharmaceuticals, Inc., San Diego, CA). It is a relatively recent bupivacaine multi-vesicular liposomal delivery system that allows slow release of bupivacaine, resulting in local anesthetic effects for up to 72-96 hours after injection. It is a safe pain control modality with a similar side effects profile to bupivacaine HCL and does not compromise breast implant integrity¹³⁻¹⁴.

Side effects of Exparel primarily includes GI upset (nausea and vomiting) which can occur in greater than 10% of patients. More rare side effects include hypotension (2-10%), insomnia (2-10%), pruritus (3%), postoperative anemia (2-10%), and muscle spasm (2-10%). Similar to other local anesthetics, dose related toxicity can occur and can lead to central nervous system excitation or depression. Exparel has a half-life of 24-34 hours and is hepatically metabolized and renally excreted. It should be used in caution with patients with moderate-severe hepatic or renal impairment because of the increased risk of toxicity. Exparel may increase the toxicity of lidocaine and bupivacaine. Bupivacaine can be administered with or immediately before Exparel as long as the milligram dose ratio of bupivacaine to Exparel is not greater than 1:2. Furthermore, Exparel may increase the effect of neuromuscular blocking agents. Exparel is not recommended in pregnant patients as there have been no studies conducted in this population and high doses used in animal models have been shown to decrease fetal

THE USE OF LIPOSOMAL BUPIVACAINE FOR PAIN CONTROL FOLLOWING MASTECTOMY AND IMMEDIATE IMPLANT BASED BREAST RECONSTRUCTION

Wake Forest Baptist Comprehensive Cancer Center
CCCWU # 99517

survival. It has been FDA approved for administration into the surgical site and the recommended a standard dosing for breast surgery of 266 mg (20 ml)²⁸.

Multi-center, randomized, double-blind, placebo-controlled, parallel-group clinical trials have been performed for Exparel use in postoperative pain control for bunionectomy and hemorrhoidectomy. In the bunionectomy trial, it was found that with injection of Exparel there was a statistically significant reduction of cumulative pain levels over the first 24 hours after surgery²⁹. Similarly, in the hemorrhoidectomy trial, it was found that the Exparel group had a decreased cumulative pain score at 72 hours³⁰.

Furthermore, liposomal bupivacaine has been shown to improve outcome measures including mean hospital stay and post-operative pain scores in a wide range of procedures from abdominal wall reconstruction to thoracotomies and sternotomies^{15,16}. In retrospective studies, the use of Exparel decreased immediate postoperative pain associated with breast reconstruction compared with IV and oral narcotics and bupivacaine pain pumps. It also showed a significant decrease in mean length of stay compared to IV and oral narcotic pain management¹⁸. Up to this point, there have been no prospective studies examining the effects of Exparel on outcome measures when used in tissue expander based breast reconstruction. We believe that its use will decrease post-operative pain and will lead to improved performance in outcome measures.

2.0 Objectives

2.1 Primary Objective(s)

- 2.1.1 The primary objective of this clinical study is to evaluate the effect of Exparel on mean postoperative pain levels in patients who have undergone mastectomy and breast reconstruction within the first 48 hours. We hypothesize that Exparel will decrease mean postoperative pain levels within the first 48 hours.

2.2 Secondary Objective(s)

- 2.2.1 To evaluate the effect of liposomal bupivacaine on cumulative pain control within the first 48 hours after mastectomy and breast reconstruction
- 2.2.2 To evaluate the effect of liposomal bupivacaine on the amount of postoperative narcotic use after mastectomy and breast reconstruction for the first month after surgery
- 2.2.3 To evaluate the effect of liposomal bupivacaine on length of hospital stay after mastectomy and breast reconstruction
- 2.2.4 To evaluate the effect of liposomal bupivacaine on hospital readmission rates a within 2 months after mastectomy and breast reconstruction
- 2.2.5 To evaluate the effect of liposomal bupivacaine on the occurrence of opioid adverse effects within the first week of surgery after mastectomy and breast reconstruction
- 2.2.6 To evaluate the effect of liposomal bupivacaine on the trajectory of postoperative pain control within 2 months after mastectomy and breast reconstruction

THE USE OF LIPOSOMAL BUPIVACAINE FOR PAIN CONTROL FOLLOWING
MASTECTOMY AND IMMEDIATE IMPLANT BASED BREAST RECONSTRUCTION

Wake Forest Baptist Comprehensive Cancer Center
CCCWU # 99517

3.0 Patient Selection

3.1 Inclusion Criteria

- 3.1.1 All patients who receive a bilateral mastectomy with only immediate sub-pectoral implant based breast reconstruction
- 3.1.2 Age \geq 18 years
- 3.1.3 Ability to understand and the willingness to sign an IRB-approved informed consent document.
- 3.1.4 Patients who receive tissue expander placement or direct permanent implant placement will be included in the study.
- 3.1.5 ASA patient status I-III patients

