6.1 Study-Related Activities

Patient involvement in the study will be initiated in the plastic surgery clinic. Eligible subjects will be identified prior to surgery. Potential subjects will be contacted either by phone or during their clinic visit, informed consent will be obtained and a 30-minute preoperative assessment will be performed. Patients will be informed that if they are expected to undergo an axillary lymph node dissection at the time of surgery then they will be excluded from the study. Patients who are undergoing sentinel lymph node biopsies will be included in the study, but if their nodes are positive and there is an intraoperative decision to pursue axillary lymph node dissection they will subsequently be excluded from the study. Also, we will record demographic and history information, including existing pain elsewhere, and administer questionnaire-based measures of psychological state, physical function, and baseline pain (Table 1, Appendix F). Questionnaire responses will be entered via the cancer center REDCap data entry form. From these questionnaires, we will place each participant on a dimensional continuum that describes their general cognitive style. We will use multidimensional scaling (MDS) to force catastrophizing and optimism as 2 ends of this continuum.

Table 1. Preoperative Questionnaires

Life Orientation Test-Revised (LOT-R)

PROMIS- Depression

PROMIS- Anxiety

Pain Catastrophizing Scale (PCS)

**THE USE OF LIPOSOMAL BUPIVACAINE FOR PAIN CONTROL FOLLOWING
MASTECTOMY AND IMMEDIATE IMPLANT BASED BREAST RECONSTRUCTION**

Wake Forest Baptist Comprehensive Cancer Center
CCCWU # 99517

[figure not shown]
These two constructs describe cognitive styles that are strongly inversely associated with each other; MDS will provide the optimal weights to best order individuals on this latent scale. Studies have examined the interplay of these constructs with other psychological concepts such as acceptance, pain-related disability and psychosocial adjustment and have found that both are reliably associated with the positive and negative aspects of the adjustment to pain.

The research coordinator will then assign the patients a study number. On the day of surgery, each patient will be randomized to be in one of the following two groups for perioperative local anesthetic infiltration:

1. Local infiltration of bupivacaine
2. Local infiltration of liposomal bupivacaine

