The study will be double blinded to both patients and providers including plastic and general surgeons involved in their operative care. We will enroll our patients in pharmacy randomization program, in which the pharmacy will deliver the appropriate medication per assigned group.

To monitor our primary outcomes, patients will be asked to rate their pain level on a visual analog scale (Table 2, Appendix Z) with activity every 12-hours after surgery during their post-procedure stay. The activity for which they will rate their pain will be the arm movements associated with eating. In the hospital, their visual analog scores will be provided to each patient in person by their nurse every 12 hours. Subject's pain scores will continue to be recorded every 12 hours via a phone call from a study team member for the first 48 hours after discharge. Additionally, while in the hospital, the amount of narcotics used will be recorded and converted into morphine equivalents.

Upon discharge, patients will be given a sheet to record their pain level and the amount of narcotics & benzodiazepines used (Appendix K). Both the amount of narcotics & benzodiazepines and the pain level are to be reported at the time of taking any narcotics & benzodiazepines. Patients will follow up with our clinic at 1 week, 3 weeks, and 5 weeks postoperatively. At week 1 patients will bring in their medication and pain diary, and fill out a pain assessment (Appendix G) in addition to a questionnaire assessing breast cancer surgery

THE USE OF LIPOSOMAL BUPIVACAINE FOR PAIN CONTROL FOLLOWING MASTECTOMY AND IMMEDIATE IMPLANT BASED BREAST RECONSTRUCTION

Wake Forest Baptist Comprehensive Cancer Center
CCCWU # 99517

disability (Appendix H)²³. During subsequent appointments made at 3 and 5 weeks postoperatively, they will be assessed and receive the pain assessment and breast cancer surgery disability assessments as well. When tissue expansion is initiated will be determined by the primary surgeon, but we will track the dates of the initiation of expansion as this will impact pain scores within the electronic medical record.

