10.0 Statistical Considerations

10.1 Analysis of Primary Objective

10.1.1 The study will allow for an attrition rate of 10%. Assuming a similar standard deviation in pain score at 48 hours for the local infiltration of liposomal bupivacaine and bupivacaine arms, with a 2-sided alpha of 0.05 and power of 80%, the study would have the ability to detect an effect size (absolute value of difference in sample means divided by the standard deviation) of 0.6 between the 2 groups with 25 subjects per arm. We will recruit 25 subjects per arm; if there is no attrition, with the same alpha and power as above, the study would have the ability to detect an effect size of 0.57. The primary outcome will be the pain score observed at 48 hours. To test for differences in these scores between the 2 arms, an independent t-test will be used; if the observed p-value is <0.05, statistical significance will be assumed. Two-sided ANOVA will be performed for statistical analysis once data collection is complete.

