10.2 Analysis of Secondary Objective

10.2.1 For the area under the curve of pain scores at 48 hours, prior studies have found that the area under the curve for pain scores at 72 hours for liposomal bupivacaine infiltration is $441 +/- 182$ and for bupivacaine infiltration is $461 +/- 181^{20}$. A sample size of 40 in each group will have 80% power to detect a difference in means of approximately 25% (115 units) between a Bupivacaine mean, m_1 , of 461 and a Liposomal Bupivacaine mean, m_2 , of 346 assuming that the common standard deviation is 181 using a two group t-test with a 0.05 two-sided significance level. Our study will be powered to detect this difference; we will use an independent t-test to assess statistical significance.

10.2.2 For postoperative narcotic use, prior studies have found the average use of morphine equivalents at 48 hours after mastectomy and tissue expander placement is 3.3¹⁷. This study will also have the ability to detect an effect size of 0.6 between groups, with 45 per group, a two-sided alpha of 0.05, and 80% power. We would expect the patients treated with liposomal bupivacaine to be have a lower average use. We will use an independent t-test to test for differences between groups; if the data are not normally distributed, a log transformation will be used prior to using the t-test.

10.2.3 For length of stay, the reported LOS has been shown to be 41-47 hours on average²¹. We believe Exparel will shorten this time; the study will have the ability to detect an effect size of 0.60 between the 2 groups. We will use an independent t-test to test for differences between groups; if the data are not normally distributed, a log transformation will be used prior to using the t-test.

10.2.4 For readmission rates, patients who underwent tissue expander breast reconstruction have a readmission rate of approximately 4.34%²². We anticipate a readmission rate of approximately 2%. Our study is not powered to detect differences in the 2 arms in this parameter.

10.2.5 For opioid related adverse effects, we predict a 50% incidence of opioid related adverse events in our study. With 45 per group, our study is not powered to detect differences between the 2 arms unless the difference is much larger than anticipated. With a 60%

THE USE OF LIPOSOMAL BUPIVACAINE FOR PAIN CONTROL FOLLOWING
MASTECTOMY AND IMMEDIATE IMPLANT BASED BREAST RECONSTRUCTION

Wake Forest Baptist Comprehensive Cancer Center
CCCWU # 99517

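### The narcotic-use comparison pools expander and direct-implant patients without adjusting for reconstruction type, which the protocol itself says affects narcotic use: a modest, cheaply recovered loss of precision

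*Combined protocol and SAP*

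**What the plan says.** - **Eligibility (3.1.4):** "Patients who receive tissue expander placement or direct permanent implant placement will be included in the study".
- **Background (1.0):** "Tissue expander based techniques in particular lead to even higher narcotic use and morphine equivalents than single staged implant reconstruction". This gives a direction but no size, and it concerns narcotic use.
- **Randomisation (6.1):** "On the day of surgery, each patient will be randomized to be in one of the following two groups", and "We will enroll our patients in pharmacy randomization program". No stratification factor, blocking or minimisation is described.
- **Primary analysis (10.1.1):** "To test for differences in these scores between the 2 arms, an independent t-test will be used". The same paragraph adds "Two-sided ANOVA will be performed for statistical analysis once data collection is complete", without naming factors or covariates.
- **Narcotic use (10.2.2):** "We will use an independent t-test to test for differences between groups", after a log transformation if the data are not normal. Length of stay (10.2.3) is handled the same way, and the pain AUC (10.2.1) also by t-test.
- **Expansion (6.1):** "we will track the dates of the initiation of expansion as this will impact pain scores". No analysis uses these dates.
- **Covariates:** the only mention is in the trajectory analysis (5.2.6.3 and 10.2.6.2), where predictive factors are to be explored in the whole population. Reconstruction type is not named.
- **Recording of type:** the eligibility checklist (Appendix A) has a single item covering either type. The registration form (Appendix B) and the data list in 9.0 have no field for it.

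**The concern.** The plan identifies a baseline characteristic that predicts one of its secondary outcomes, admits patients on both sides of it, and then leaves it out of both the randomisation and the analysis. Two consequences follow in a trial of 50. The difference between types stays in the error variance of the t-test. And if the arms happen to differ in their share of expanders, the estimated treatment difference moves with that imbalance, with no planned correction. An adjustment added after an imbalance has been seen would be open to challenge, so the choice needs to be made in advance.

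**Working it through.** **Inputs from the documents.** 25 per arm, 50 in total (10.1.1, 10.3); two-sided alpha 0.05; target effect 0.6 SD (10.1.1, 10.2.2); 45 per group quoted for narcotic use (10.2.2).

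**Inputs assumed, because the documents do not give them.** Expander share p from 0.5 to 0.9. Difference between types g from 0.25 to 1.0, in units of the SD within type.

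**1. The plan's own figure.** Noncentral-t power of a two-sample t-test at 0.6 SD:
- 45 per group: 80.4%, which matches 10.2.2.
- 25 per arm: 54.7%, not the 80% given in 10.1.1 and 10.3. The effect detectable with 80% power at 25 per arm is 0.81 SD.

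The sample-size discrepancy is a separate matter. It is used here only to set the baseline: 25 per arm and 54.7%.

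**2. Chance imbalance.** With simple randomisation, the between-arm difference in expander share has SD = √(2p(1−p)/25). The probability of a difference of 20 points or more (5 or more patients of 25) comes from the exact difference of two Binomial(25, p) counts.

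| p | SD of difference | P(difference ≥ 20 points) |
|---|---|---|
| 0.5 | 14.1 points | 20.3% |
| 0.7 | 13.0 points | 16.4% |
| 0.8 | 11.3 points | 11.0% |
| 0.9 | 8.5 points | 3.4% |

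**3. Shift from a 20-point imbalance.** Shift = 0.20 × g, which is 0.05 SD at g = 0.25, 0.10 SD at g = 0.5 and 0.20 SD at g = 1.0. Against the 0.6 SD target that is 8%, 17% and 33%. The standard error of the arm difference is √(2/25) = 0.28 SD, so each shift is below one standard error.

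**4. Variance left in the error term.** Total variance / within-type variance = 1 + g²p(1−p).
- Smallest (g = 0.25, p = 0.9): 1 + 0.0625 × 0.09 = 1.006.
- Largest (g = 1.0, p = 0.5): 1 + 1 × 0.25 = 1.25.

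**5. Power at 25 per arm.** Take the effect as 0.6 within-type SD. The unadjusted test has effect size 0.6/√(1 + g²p(1−p)) and 48 degrees of freedom. The adjusted test has effect size 0.6 and 47. The small extra variance that an imbalanced covariate causes in the adjusted test is ignored.

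| g | Adjusted | Unadjusted, p = 0.9 | Unadjusted, p = 0.5 | Loss (points) |
|---|---|---|---|---|
| 0.25 | 54.7% | 54.5% | 54.1% | 0.2-0.6 |
| 0.5 | 54.7% | 53.8% | 52.3% | 0.9-2.4 |
| 1.0 | 54.7% | 51.2% | 46.0% | 3.5-8.7 |

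If the 0.6 refers instead to the total SD, the unadjusted test has 54.7% and adjustment raises it to between 54.9% and 64.2%.

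**6. Type I error.** In 100,000 simulated trials per setting with no treatment effect, the unadjusted t-test rejected in 5.0% (p = 0.5, g = 1.0) and 4.9% (p = 0.7, g = 0.5).

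**The case against.** An unadjusted t-test is a legitimate analysis of a randomised trial. The variation caused by reconstruction type is already in its standard error, and the type I error simulation confirms this. A 20-point imbalance would be absent in about 80-97% of trials over the assumed range; where it occurs, the shift is smaller than one standard error and can go either way. The protocol's wording also leans towards expanders (the background in 1.0, the description of the injection in 6.2, the benchmarks in 5.2), so the mix may lie near the end of the range where little is gained. The sample-size discrepancy costs far more power than the missing covariate. All of this stands. It limits the size of the point, but it does not explain why a predictor named in the plan is left out.

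Three stronger readings are tempting, and the documents do not support them:
- *The plan says expanders raise early pain.* It does not. The expander statement in 1.0 covers narcotic use; the pain-score comparison there is between implant and autologous reconstruction, and autologous patients are excluded (3.2.1). The remark in 6.1 concerns the start of expansion, which the surgeon times, not pain in the first 48 hours. Nor does 1.0 call the predictor strong.
- *The comparison is biased, or its error rate inflated.* Neither follows under randomisation.
- *The planned type is already on file for every patient.* The checklist shows only that one of the two applies.

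The exploratory covariate wording in the trajectory analysis does not extend to the t-tests.

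**Conclusion.** The point holds for narcotic use, as a modest loss of efficiency and a missing safeguard against chance imbalance. Under the assumed ranges, the cost at 25 per arm lies between negligible (0.2 points of power; 3.4% chance of a 20-point imbalance) and moderate (8.7 points; 20.3%). The upper end needs both an even mix and a type difference of a full within-type SD, and nothing in the documents shows that either applies. The calculations take all 25 per arm as evaluable and a common treatment effect in both types. For the primary pain score and length of stay, a device effect is a reasonable inference only. The improvement is worth making because it is cheap and because total recruitment is set at 50 (10.4), which leaves few other ways to gain precision.

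**What to change.** 1. Split the combined expander/implant item in Appendix A into two options, so that the planned type is recorded for each patient before randomisation.
2. In 10.2.2, replace the t-test with a linear model (ANCOVA) containing arm and planned reconstruction type, on the log scale where the plan calls for that transformation.
3. Use the same covariate in the primary pain model (10.1.1) and in length of stay (10.2.3), and state there that its inclusion rests on inference. If the ANOVA sentence in 10.1.1 is kept, name its factors.
4. Analyse by planned type, even if the operation changes. Do not adjust the arm comparison for the date on which expansion starts, since that follows randomisation.

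Stratified randomisation is not needed for this. The cost is one form field, one degree of freedom and a few sentences of SAP wording. If nearly all patients turn out to receive expanders, little is gained and almost nothing lost.
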